Finally, IRRs have been hypothesized to be a reaction by autoantibodies to the treatment drug or possibly from the release of cytokines from CD20 expressing cells as they are destroyed by ocrelizumab causing a “cytokine storm”. Understanding this process may lead to mechanisms that may aid in ameliorating these infusion reactions. If they are associated with ADA, then it might be possible to predictively premedicate these patients only. Alternatively, if they are associated with cytokine release, it may be possible to eliminate premedication in patients who are already CD20⁺ cell depleted in subsequent infusions. Therefore, we will assay the profile of certain cytokines in the serum 4 hours after start of ocrelizumab infusion.

Since ocrelizumab has entered the market, third party payers within and outside the US have required that the FDA or EMA approved versions of anti-CD20 monoclonal antibodies be used in the treatment of MS, namely ocrelizumab. Currently, we estimate several thousand MS patients in the US and Sweden are taking rituximab currently. Thus, it will be important to demonstrate that switching from a chimeric anti-CD20 to a more fully humanized anti-CD20 does not lead to unexpected infusion reactions and does not increase the probability of development of anti-drug antibodies.

The Rocky Mountain MS Center (RMMSC) at the University of Colorado Anschutz Medical Campus prescribed rituximab infusions for 533 MS patients in the last 12 months, of which 323 patients received their infusion at the University of Colorado Hospital's Outpatient Infusion Center between September, 2015-March, 2016. The RMMSC is one of the few sites nationwide with large numbers of MS patients treated with rituximab. On March 28, 2017, Ocrevus (ocrelizumab) was approved by the FDA for the treatment of primary progressive and relapsing multiple sclerosis. With the approval of ocrelizumab, current rituximab users are being counselled by their MS providers at RMMSC to consider switching to ocrelizumab if it is the only anti-CD20 MAB covered by their insurance.

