3.3 Outcome Measures

3.3.1. Primary Outcome Measure

Primary endpoint:

- a. Primary endpoint: The primary end point will be proportion of infusions with ≥ 1 IRR between the switching and comparator groups.
- b. Secondary IRR assessments:
 - a. We will also report the difference in the total number of IRRs after each infusion of ocrelizumab in the switching group compared to similar rituximab infusions in the comparator group.
 - b. The difference in proportion of patients with ≥ 1 IRR across any of their infusions between the switching and comparator groups
 - c. We will also compare the proportion of patients with an IRR following day 1 infusion versus the proportion of patients with an IRR at day 15 and month 6 infusions of ocrelizumab in the switching group.
 - d. The severity of IRRs will be assessed following each infusion of ocrelizumab in the switching and comparator group using the National Cancer Institute's Common Terminology for Adverse Events Scale.⁶ The frequency of each severity grade of IRR will be compared in a similar fashion.

Nursing staff at the University of Colorado's Outpatient Infusion Center will be responsible for classifying the severity of an IRR for each patient at the end of every ocrelizumab and rituximab infusion using the scale below. Nursing staff will be asked to record the highest grade of an IRR that they observed or intervened upon for each patient after completion of their infusion.

Severity of IRR:

Grade 0: No infusion reaction

Grade 1: Mild reaction (transient flushing or rash drug fever < 38 degrees C); infusion interruption not indicated; intervention not indicated

Grade 2: Requires therapy or infusion interruption but responds promptly to symptomatic treatment (e.g., antihistamines, NSAIDs, narcotics); prophylactic medications indicated for 24 hours.

Grade 3: Prolonged (i.e., not rapidly responsive to symptomatic medication and/or brief interruption of infusion); recurrence of symptoms following initial improvement; hospitalization indicated for other clinical sequelae (e.g., renal impairment, pulmonary infiltrates)

Grade 4: Life threatening consequences; urgent intervention indicated.

Grade 5: Death

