4. MATERIALS AND METHODS

4.1 Subjects

We plan to enroll 100 patients in the switching group and between 100 and 200 patients in the comparator group (to study 200 infusions) for a total of up to 200-300 patients which would provide adequate power (90%) for the study. To account for screen failures and withdrawals, we are seeking to enroll an additional 50 patients for a total of 250-350 patients. Patients are not confined to only one of the 2 groups. For example, data may be collected from a patient as part of the rituximab arm and then at a later point the patient decides to switch to ocrelizumab. This patient could then be consented into the switching group. Enrollment will occur over a 3-month period at RMMSC.. Dropouts in the switching group that occur prior to the 6 month infusion will be replaced. All patients will be included in the analyses (Intent to Treat Analysis).

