4.2 Method of Treatment Assignment

The study will not be a randomized trial. Patients will not be assigned to the switching group, but rather will be enrolled after a clinical decision has been made with their provider about whether they will continue on rituximab or switch

to ocrelizumab. The following steps will be taken to minimize potential biases in sample selection.

First, in an effort to impose some degree of similarity between the treatment groups, control patients will be matched, either 1:1 or 2:1 depending on the number of control patients, with switching patients on gender and age (+/- 2 years) at recruitment. The demographic information on switching patients will be scanned to find matches for the patients in the non-switching group.

Furthermore, screening of additional patients beyond the 200 required for enrollment in the non-switching group will be also conducted to ensure the best possible matches. Second, baseline statistics will be monitored as patients enter the study, and selection of patients may be modified in order to maintain relative balance between treatment groups (if necessary using measures of disease severity other than age and gender) if we are able to overenroll the number of non-switchers. Third, demographic variables and measures of baseline disease severity, including age, gender, MS disease duration, type of MS at baseline (first infusion in both study groups), along with discontinuations, will be recorded and compared between treatment groups.

All available observations will be used. For continuous variables (age, MS disease duration), by treatment group means, standard deviations, medians, and ranges will be recorded, and differences among treatment groups will be tested for with either with T-test/ANOVA methods or Wilcoxon/Kruskal Wallis tests. For categorical variables (gender, type of MS, disability, discontinuations), frequencies and proportions will be presented, and differences among treatment groups will be tested for using chi-square/Fisher's exact test. Fourth, following these measures, if treatment confounding is found to still be an issue, regression or propensity score methods, with covariates such as age, MS disease duration, and baseline EDSS score will be used post hoc to minimize confounding.

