4.5.1 Assessments during Treatment

The following evaluations will be conducted during and post treatment:

Study Visits and Procedures Summary:

Study visits for the switching group include a) screening visit, b) first infusion of 300 mg of ocrelizumab (day 1 or T₀), c) 300 mg of ocrelizumab infusion on day 15 (T₁), d) 600 mg of ocrelizumab at 6 months (+/- 2 weeks) after day 1 (T₂) and, e) a research termination visit between month 12 and 18 - (+/- 2 weeks)(T₃). In some cases, screening procedures may be performed on the first infusion day rather than as a separate visit. The patient may continue on 600 mg of ocrelizumab or (if the patient prefers) 500mg rituximab at T₃, or 12 to 18 months after Day 1 (T₀). A month is defined as 28 days. Study visits for the comparator group include only standard of care infusion of rituximab, up to two infusions per patient, approximately 6 months apart. Research data on IRRs for the comparator group will be collected from the medical records.

A summary of all procedures for switching group is outlined under “Schedule of Events” in **Table 1** below. During the screening visit, patients will be consented for the study and receive both a medical and full neurological exam. Verification of their hepatitis B and C status including testing will be conducted if a patient has not been tested in the last two years. MS disease history and demographic information will also be collected. Patients will also receive an EDSS exam and take an online version of the PDDS (done as standard of care- on an iPad).

The Expanded Disability Status Scale (EDSS) is a commonly used assessment that allows clinicians to objectively measure changes in the disability status of MS patients using unbiased clinical raters.⁷ The **EDSS** provides a total score on a scale that ranges from 0 to 10. The first levels 1.0 to 4.5 refer to people with a high degree of ambulatory ability and the subsequent levels 5.0 to 9.5 refer to the loss of ambulatory ability. The range of main categories include (0) = *normal neurologic exam*; to (5) = *ambulatory without aid or rest for 200 meters; disability severe enough to impair full daily activities*; to (10) = *death due to MS*. In addition, it also provides seven subscale measurements called Functional System (FS) scores.

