(generalized linear mixed models) methods to incorporate correlation on repeated infusions on a patient. The same method will apply to other longitudinal binary outcomes. Poisson or negative binomial models with exposure terms could calculate rates of IRR per infusion per patient as a counting process. Similar methods will be used to compare IRR rates between the switching group and OPERA I and II phase 3 clinical trials. The total number of IRRs experienced in each patient, will be analyzed with Poisson or negative binomial models. Paired T tests will be used to assess differences in specific cytokine markers between pre and post infusion at each infusion cycle. Patient reported outcomes will also be reported descriptively. Frequencies and proportions will be reported for adverse and serious events and loss to follow up

As contingency methodology, exact tests and confidence intervals for measures of association between categorical variables can be utilized when necessary, if the sample sizes for some of the cells are small. Transforms or rank based methods, such as Wilcoxon sign rank, can be used in place of the T-test if deviation for normality is severe. Otherwise the T-test is a robust test of mean differences for medium to large sample sizes. If matching leads to good balance between the treatment groups on the demographic and disease variables, including age, MS disease duration, and baseline PDDS score, then confounding will not be an issue and the proposed unadjusted tests should be adequate. Alternatively, if the demographic and disease variables are not balanced, then regression or propensity score methods will be used to adjust for potential confounding. Sensitivity analysis comparing unadjusted and adjusted results will be used to determine the extent of the confounding effect. Adjustment for covariates can sometimes improve the precision of the estimated treatment difference by reducing random noise in the outcome.

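### Comparators are matched on gender and age, but these factors are not carried into the primary per-infusion comparison, so the matched balance can be lost if comparator infusions per switcher vary with them

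*Combined protocol and SAP*

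**What the plan says.** **Matching.** Section 4.2 states that "control patients will be matched, either 1:1 or 2:1 depending on the number of control patients, with switching patients on gender and age", with age within 2 years. It also plans "screening of additional patients beyond the 200 required for enrollment in the non-switching group" so as to improve the matches. Section 4.1 sets the numbers at 100 switchers and "between 100 and 200 patients in the comparator group (to study 200 infusions").

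**Who is analysed.** Section 4.1: "All patients will be included in the analyses (Intent to Treat Analysis"). Nothing says what happens to a comparator or a switcher without a match.

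**Unit of analysis.** Section 3.3.1: "The primary end point will be proportion of infusions with" at least one IRR. Section 4.5.1 allows comparators "up to two infusions per patient, approximately 6 months apart". Section 4.9.6 expects 300 ocrelizumab and 200 rituximab infusions.

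**Model.** Section 4.9.4 offers logistic or relative-risk models with GEE and/or GLMM, to handle repeated infusions within a patient. It names no stratified, conditional, weighted or matched-set analysis.

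**Adjustment.** If matching leaves the groups well balanced, Section 4.9.4 concludes that "confounding will not be an issue and the proposed unadjusted tests should be adequate". If not, regression or propensity scores follow. The variables named are age, MS duration and baseline PDDS in 4.9.4, and age, MS duration and baseline EDSS in 4.2. Both lists are open-ended, and gender is in neither. Sections 4.2 and 4.9.2 do test gender between the groups at baseline.

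**The concern.** Matching is the first control on selection bias listed for a non-randomised comparison. It protects a crude comparison when comparator infusions are spread over switchers in a way unrelated to age and gender. A single ratio with equal infusion counts does this, but the plan does not fix either one. A comparator total strictly between 100 and 200 implies a mixed ratio if all 100 switchers are matched. If patients of one gender or age band are easier to match, or return more often for a second infusion, the pooled rituximab rate is weighted towards them.

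The only planned protection in the analysis is conditional. It starts when balance is judged not good, and that term has no threshold. A baseline test at this sample size has little power against a moderate imbalance. A residual difference in a factor the design set out to control could then remain in the primary estimate.

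**Working it through.** **1. The plan's own figure.** Inputs from Section 4.9.6: 14.3% against 34.3%, 95 per group, two-sided alpha 0.05.
- Pooled proportion: (0.143 + 0.343)/2 = 0.243.
- SE under the null: √(2 × 0.243 × 0.757/95) = 0.0622.
- SE under the alternative: √((0.143 × 0.857 + 0.343 × 0.657)/95) = 0.0605.
- Power: Φ((0.200 − 1.96 × 0.0622)/0.0605) = Φ(1.29) = 90.1%.

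The stated 90% is reproduced, and this point does not change it.

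**2. How the gender mix can move.** Assumption, not in the documents: 70 of 100 switchers are women. Let a and b be the fractions of women and men who get a second comparator. The share of women among comparators is

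s = 70(1 + a) / [70(1 + a) + 30(1 + b)].

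With no drug effect, the spurious difference (ocrelizumab minus rituximab) is (0.70 − s) × g, where g is the assumed IRR gap, women minus men.

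| a, b | Comparators | Share of women | g = 5 points | g = 10 | g = 20 |
|---|---|---|---|---|---|
| 0, 0 or 1, 1 (uniform) | 100 or 200 | 70.0% | 0 | 0 | 0 |
| 0.5, 0.5 (mixed, unrelated to gender) | 150 | 70.0% | 0 | 0 | 0 |
| 0.7, 0.2 | 155 | 119/155 = 76.8% | −0.3 | −0.7 | −1.4 |
| 1, 0 (only women doubled) | 170 | 140/170 = 82.4% | −0.6 | −1.2 | −2.5 |
| 0, 1 (only men doubled) | 130 | 70/130 = 53.8% | +0.8 | +1.6 | +3.2 |

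If the gap runs the other way, every sign reverses. With 60% or 80% women among switchers, the extremes stay within about 3.4 points.

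**3. Infusion counts alone.** At a uniform ratio, two infusions per woman and one per man gives (0.7 × 2)/(0.7 × 2 + 0.3 × 1) = 82.4% of comparator infusions from women.

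**4. Would the baseline test catch it?**
- Moderate case, 70/100 against 119/155: pooled share 189/255 = 0.741, SE 0.0562, z = 0.0677/0.0562 = 1.21, p = 0.23. Power to detect such an imbalance: Φ((0.0677 − 1.96 × 0.0562)/0.0570) ≈ 23%.
- Extremes: 70/100 against 140/170 gives p = 0.018, and 70/100 against 70/130 gives p = 0.013. At 0.05, both would be flagged.

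**5. Effect on the test.** Null simulation, one observation per patient, 40,000 runs, assumed IRR risks of 18% and 6%, or 20% and 2%, in women and men:
- Uniform ratio or mix unrelated to gender: unadjusted type I error 4.5% to 4.9%.
- Moderate case: 5.0% to 5.2%.
- Extremes: 5.4% to 9.4%.
- Stratified by gender, every scenario: bias about 0.0 points, type I error 4.8% to 5.1%.

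**The case against.** **A mixed ratio is not stated.** A reader might infer that matching at 1:1 or 2:1 necessarily brings imbalance back. The documents do not support that. The ratio depends on how many controls are available, which reads naturally as one ratio for the study. Even a mixed ratio does harm only if it, or the infusion count, follows age or gender. This stands, so the point is about what the plan permits.

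**The 200-infusion target could restore balance.** With 155 comparators, 45 must give two infusions and 110 one (90 + 110 = 200). In the moderate case exactly 45 comparators are in 1:1 sets (21 women, 24 men). If they gave the second infusions, every switcher would have two comparator infusions, and women would supply (42 + 98)/200 = 70%. The plan does not tie infusion counts to sets. If second infusions fell evenly across comparators, the share would stay at 76.8%.

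**There are safeguards.** Selection may be modified during enrolment to keep balance, gender is tested at baseline, imbalance triggers adjustment, and unadjusted and adjusted results are to be compared. A strong imbalance would be caught: 75/100 against 150/175 women gives p = 0.027. What survives is the moderate case, where the bias is also smaller.

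**The pool is not shown to be too small.** From "of which 323 patients received their infusion at the University of Colorado" a reader might infer that a 2:1 ratio, needing 300 patients, would nearly exhaust the pool and leave many switchers poorly matched. That count covers September 2015 to March 2016 and is not the pool eligible at enrolment. Section 4.1 also lets one patient contribute to both groups.

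**Conclusion.** The concern holds in a limited form. The plan matches on gender and age, then leaves both out of its default primary comparison. Gender is not named even for the fallback, although the open-ended lists would allow it. Balance can be lost if comparator infusions per switcher vary with either factor, and a moderate loss would probably go unadjusted.

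The size cannot be taken from the documents, because they give no IRR rates by gender or age. Under the assumptions shown it is of the order of 0 to 3 percentage points, in either direction, against a 20-point design difference. The upper end needs an extreme mix that the baseline test would probably flag. The moderate case that passes gives at most about 1.4 points and hardly moves the type I error.

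A reader might also infer that ignoring the matched sets makes the test invalid, or that an ocrelizumab excess would be understated. Neither follows. With a uniform ratio the crude difference is unbiased and the test slightly conservative, and the direction depends wholly on which group is assumed to react more often. This is a free improvement to the analysis and not a flaw that threatens the study.

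**What to change.** In Section 4.9.4, prespecify age and gender as covariates (or gender and age band as strata) in the primary GEE/GLMM. Apply this to all enrolled patients, regardless of the balance check. Make the unadjusted comparison the sensitivity analysis. In Section 4.2, state whether one ratio applies to the whole study or may differ between sets, and how comparators and switchers without a match are handled.

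Do not exclude unmatched patients from the primary analysis. That would conflict with the all-patients rule in Section 4.1 and could cost power. If, for illustration, 23 of 100 switchers had no match, 77 per group would give about 83% by the formula used above, against 90% at 95. An analysis weighted by matched set may be added as a sensitivity analysis if the set number is recorded.

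The cost is a few sentences of SAP text. Age and gender are already collected for the matching, and no patient, visit or sample is added.

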3. STUDY DESIGN

3.1 Description of the Study

This is a prospective *between and within group* observational study to determine differences in tolerability, immunogenicity and safety related outcomes for MS patients who have been administered at least two infusions of rituximab, with the last dose of rituximab within 12 months of screening and are willing to be switched to ocrelizumab, compared to patients who are continuing on rituximab as a comparison cohort from the clinic population treated as part of routine clinical care in our program.

The comparator arm is an observational arm only. In addition to prospective data collection, we will collect infusion-related reaction data retrospectively for infusions done after August 1, 2016 (when we began collecting infusion reactions in a standardized way as part of standard of care at the infusion center).

Retrospective data will be collected only after consent is obtained.

In a prospective evaluation with patients at RMMSC who are currently on sustained rituximab treatment for their MS, we will examine the frequency and

severity of IRRs for 100 patients who switch to ocrelizumab (**switching group**) compared to 200 patients continuing rituximab as our primary outcome (**comparator group**). Our secondary outcome is to examine anti-drug antibody formation post switching from rituximab to ocrelizumab (**switching group**). Comparisons for the both outcomes will also be made to findings from the OPERA I and II randomized clinical trials. Other exploratory outcomes including the measurement of B cell reconstitution, cytokine reactions and adverse event profiles will also be examined.

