Potential study patients will be identified from RMMSC electronic medical records (EPIC) using the study inclusion and exclusion criteria. Patients will be recruited by the study coordinator through the University of Colorado's Outpatient Infusion Center. Potential patients are already being identified through their MS providers at RMMSC with whom discussions about the possibility of switching to ocrelizumab are currently underway. Study participants who complete the observation phase of the study will be offered the ability to continue to receive ocrelizumab infusions provided for free by Genentech until ocrelizumab is approved and available to them through their health insurance plan. Once ocrelizumab is available by prescription they will receive priority for assistance through the Genentech/Roche Patient Assistance Program for Ocrelizumab for out of pocket expenses. Ocrelizumab will be provided through priority placement in Genentech's patient assistance program for those patients who are not able to receive insurance coverage for it.

MS patients included in this study will have made a decision with their provider to either stay on rituximab or to switch to ocrelizumab outside of this study. The decision to switch to ocrelizumab or to stay on rituximab will be made as part of

the clinical treatment process between the patient and his/her provider based on his/her disease severity and suitability for treatment among other factors. Therefore, patients are not randomized into either treatment arm. For the group that stays on rituximab, participation in this study is purely observational. For those patients in the rituximab arm who are deemed to be appropriate candidates for switching to ocrelizumab, the option to do so will be provided as standard of care under priority access and/or patient assistance programs (contingent on their individual health insurance status).

It is important to note that because the incidence of IRRs for infusions prior to enrollment are not collected prospectively for those continuing treatment with rituximab and because adverse events including IRRs will not be collected using the same methods for each treatment group following enrollment, interpretation of any difference in the incidence of these events will be limited.

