4.9.4 Safety Analysis

The default analysis will be available case for all eligible participants on an intent to treat basis. Alpha = 0.05 for all tests. As in the OPERA I and II randomized clinical trials, the primary and secondary end points will be descriptively presented. Frequencies and percentages for the severity of IRR grades (Grades 0-5) will be presented for both study groups following each infusion time point and overall between groups. 95% confidence intervals for the proportions will be calculated. Differences in the distribution of IRR severity grades between independent samples (i.e. comparison between groups at a common time point) will be tested with the chi-square or Fisher's exact association test, and additionally with ordinal or multinomial logistic regression. If sample sizes are small among some levels of IRR severity grades, they may be collapsed or dichotomized (i.e. Grade 3 or higher, any reaction or no reaction, severe reaction or none as examples) and methods described for binary outcomes under secondary endpoints will be utilized. Dichotomization may be used to make analysis and presentation of results more manageable as well.

The primary endpoint will be the proportion of whether any IRR occurred (yes or no) per infusion cycle per patient in each study group. The secondary endpoints include the proportion per infusion per patient of severe infusion reaction (grade 3 or greater), the proportion of infusion reactions and severe infusion reaction per patient across all infusions, the proportion patients with anti-drug antibodies, and the proportion of patients with depleted B cells. The primary outcome, binary occurrence of IRR per infusion per patient, could be analyzed with logistic or relative risk models, with GEE (generalized estimating equations) and/or GLMM

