4.9.6 Determination of Sample Size

The sample size will be a convenience sample. It is anticipated a minimum of 100 patients will qualify for each cohort (200 total) resulting in studying 300 infusions with ocrelizumab and 200 infusions with rituximab. This is an observational study not designed to demonstrate superiority of ocrelizumab over rituximab in efficacy but instead indicate the magnitude of the relative tolerability and immunogenicity. The primary endpoint is the difference in the percentage of IRRs between the two study groups. In addition, both study groups will include treatment experienced patients on rituximab who have experienced a minimum of two infusions and either continue to stay on rituximab or switch to ocrelizumab.

To estimate study power with the proposed sample size of 100 infusions in each group, we conducted a chart review of 50 patients at the Rocky Mountain MS Center who are currently taking rituximab and examined their IRRs using the proposed IRR grading scale (see section 3.3.1) from Grade 0-5. The number and severity of IRRs were captured following their third rituximab infusion. The highest grade of an IRR that occurred during the infusion was recorded. Our pilot data revealed that following the third rituximab infusion, 14.3% of patients had an IRR of which 85.71% were Grade 0, 12.24% were grade 2 and 2.05% were Grade 3. Hauser et al., found that following the second infusion of rituximab in patients, the majority of whom (60%) were not taking a DMT for 6 months prior to initiating rituximab only 20.3% experienced in an IRR.³

Using IRR estimates from our pilot data and establishing a clinically meaningful difference of 20% increase in IRRs, we conducted the following power analysis for a sample of 95 patients (assuming a 5% attrition rate after recruiting 100 patients in each study group). An IRR proportion for ocrelizumab users at 34.3% compared with 14.3% for rituximab (obtained from our pilot data) for a two sided (alpha = 0.05) two sample proportion test for the null hypothesis of no difference between rituximab and ocrelizumab in proportion of IRRs would result in 90% power for 95 patients per group.

In response to the FDA IND letter, “the power analysis in Section 4.9.6 of the protocol appears to compare the infusion-related reaction (IRR) rate at the third rituximab infusion (14.3%) to that of the first infusion of OCR (34.3%). Because

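### No rule fixes, independently of the charted IRR grade, which controls and which of their rituximab infusions enter the primary comparison

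*Combined protocol and SAP*

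**What the plan says.** Combined protocol and SAP:

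- **Finding patients (4.2).** "Potential study patients will be identified from RMMSC electronic medical records (EPIC) using the study inclusion and exclusion criteria".
- **Matching (4.2).** Controls are matched to switchers on gender and age (within 2 years), 1:1 or 2:1 depending on how many controls there are. Extra patients are screened to improve the matches. As a second step, baseline statistics are watched during accrual and "selection of patients may be modified in order to maintain relative balance between treatment groups". That step may use other severity measures if needed, and applies only if non-switchers can be over-enrolled.
- **Past infusions (3.1, 4.1.2).** Besides prospective collection, "we will collect infusion-related reaction data retrospectively for infusions done after August 1, 2016", after consent. The comparator inclusion criteria use an and/or, so a patient may contribute past infusions only.
- **Infusions per patient (4.1, 4.5.1).** Comparator visits are standard rituximab infusions, "up to two infusions per patient, approximately 6 months apart". The target is 200 infusions from 100 to 200 patients.
- **Where the grade is (4.5.1).** Nurses record the IRR after each rituximab infusion as routine care, and the comparator IRR data are taken from the medical record.
- **Switching group (4.5.1).** Infusions are Day 1 (T0), Day 15 (T1) and 6 months (T2), all after entry.

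**The concern.** The primary endpoint (3.3.1) is the proportion of infusions with at least one IRR, compared between groups. On the ocrelizumab side the schedule decides which infusions count. On the rituximab side people decide, and for retrospective infusions they work in a record that already holds the outcome. Any tendency to take clean infusions, or memorable ones with a reaction, would shift the comparator rate directly. It need not be deliberate: an open choice made with the answer in view is enough.

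The regression and propensity methods in 4.2 and 4.9.4 adjust for patient characteristics. They do not address selection on the outcome itself.

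**Working it through.** **1. The plan's own figure.** Inputs from 4.9.6: "An IRR proportion for ocrelizumab users at 34.3% compared with 14.3% for rituximab", a "two sided (alpha = 0.05) two sample proportion test", which "would result in 90% power for 95 patients per group". With pooled variance under the null:

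- Mean proportion = (0.343 + 0.143)/2 = 0.243.
- Null SE = sqrt(2 × 0.243 × 0.757/95) = 0.0622; critical difference = 1.96 × 0.0622 = 0.1220.
- Alternative SE = sqrt((0.143 × 0.857 + 0.343 × 0.657)/95) = 0.0605.
- z = (0.200 − 0.1220)/0.0605 = 1.29, so power = 0.901.

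The stated 90% reproduces. This point does not change it.

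**2. How open the choice is.** 200 infusions from 100 patients is 200/100 = 2 each; from 200 patients it is 200/200 = 1 each. The number of controls, the matching ratio, the number of infusions per control and the past/future mix are all left open. No section names an index date or an order such as first, latest or nearest.

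**3. Sensitivity of the comparator rate.** The documents do not give these assumptions:

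- the true comparator rate p is 14.3%;
- r is the chance that an infusion with an IRR is taken, relative to one without;
- s is the share of comparator infusions that are retrospective;
- infusions are independent.

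The rate among selected retrospective infusions is q = rp/(rp + 1 − p), and the observed rate is s·q + (1 − s)·p. Example, r = 0.75 and s = 1: 0.75 × 0.143/(0.75 × 0.143 + 0.857) = 0.10725/0.96425 = 11.1%.

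| s | r | Observed comparator rate | Apparent difference from 34.3% (points) | Rejection probability, 95 per group | Error if both true rates are 14.3%, 95 per group | Same, 300 vs 200 infusions |
|---|---|---|---|---|---|---|
| 100% | 0.5 | 7.7% | 26.6 | 99.6% | 30.6% | 62.2% |
| 100% | 0.75 | 11.1% | 23.2 | 97.3% | 10.1% | 17.3% |
| any | 1 | 14.3% | 20.0 | 90.1% | 5.0% | 5.0% |
| 100% | 1.25 | 17.3% | 17.0 | 77.0% | 8.6% | 15.0% |
| 100% | 2 | 25.0% | 9.3 | 28.7% | 46.0% | 84.7% |
| 50% | 0.5 | 11.0% | 23.3 | 97.5% | 10.5% | 18.4% |
| 50% | 2 | 19.7% | 14.6 | 62.5% | 16.6% | 35.7% |

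With s = 0 or r = 1 there is no distortion. The last column ignores correlation between infusions in the same patient.

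**4. Why adjustment does not help.** The formula for q is the same as q/(1 − q) = r × p/(1 − p): selection multiplies the comparator odds by r. If selection depends on the grade alone, this holds within every covariate stratum. With s = 1 the ocrelizumab-to-rituximab odds ratio is therefore multiplied by 1/r, adjusted or not: 1/0.75 = 1.33, and 1/0.5 = 2.

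**The case against.** The best case for the plan has five parts.

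- **Selection changes depend on baseline data.** The sentence in 4.2 is triggered by baseline statistics and needs over-enrolment, and it is one of several steps meant to reduce selection bias. The search for better matches concerns age and gender. A reader might infer that the protocol lets staff select on IRR results; it does not say so. What remains is that nothing keeps the person selecting from seeing the grade.
- **Consent comes first.** Sections 3.1 and 4.5.1 delay data collection until consent. This is real but partial protection: it does not stop a chart being read at identification, and it does not govern which infusions are taken afterwards.
- **Part of the data is prospective.** For those infusions no grade exists at enrolment. This stands, and any bias shrinks with the retrospective share.
- **The cap may not apply to past infusions.** The limit of two describes comparator study visits. On one fair reading all retrospective infusions are used, which leaves no choice among them. The text does not settle this, and the 200-infusion target makes it harder to read.
- **Limits are already admitted.** Section 4.2 says interpretation is limited because past IRRs are not collected prospectively and methods differ between groups. It does not mention selection with the outcome known. The statement in 4.2 about using all available observations belongs to the baseline comparison.

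**Conclusion.** The point holds as a missing safeguard on the primary endpoint. For retrospective infusions the grade is known when controls and infusions are chosen, and no rule makes that choice independent of it. The documents do not show that biased selection is planned or has occurred.

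The size and sign of any bias are unknown, because neither r nor s can be taken from the documents. Under the assumptions above, a moderate preference (r = 0.75 or 1.25) with all data retrospective moves the comparator rate by about 3 points and raises the nominal 5% error to 10.1% or 8.6% with 95 per group.

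Two stronger readings should be resisted. A reader might take the extreme case, in which two of three infusions per control are kept with all grades in view (2.9% to 21.3%), or two of four (0.5% to 28.1%). Those ranges assume perfect selection, three or four eligible infusions for every control, and a cap that covers past infusions; the documents establish none of these. A reader might also think such bias undetectable. A comparison of retrospective with prospective comparator rates would partly reveal it.

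**What to change.** Amend 4.2 and 4.5.1, with a matching line in 4.9.4:

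1. Match controls from a list extracted without the IRR field. Freeze the matched list before any IRR grade is abstracted, and make later changes on baseline variables only.
2. Fix the counted comparator infusions by date: the eligible rituximab infusion nearest the matched switcher's Day 1 and the next one about 6 months later, past or future, whatever the grade. This also aligns calendar time between groups. State whether the two-infusion cap covers retrospective infusions.
3. Report retrospective and prospective comparator IRR rates separately, and add a sensitivity analysis using all eligible infusions.

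The cost is one extra extraction step and some protocol wording, less freedom in choosing controls, and some controls supplying only one infusion. The power calculation is untouched.

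Two gaps would remain. The hypersensitivity exclusion (4.1.3) may bring reaction history into view at eligibility review even with the IRR field removed. The date rule also does not by itself cover a comparator patient who later joins the switching group, which 4.1 allows.
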